Patients in the SDC arm will also receive a flyer with information about Relay and a telephone number they can call to receive Relay services at any time after their ED visit. While we expect few patients will call for services, DOHMH and the study investigators agree that for fairness all study participants should be offered the ability to receive Relay services if they choose to do so. DOHMH and research staff will track any Relay services provided in this patient-initiated manner. After the 12 month study follow-up period (for the primary outcome analysis) has concluded, DOHMH will contact participants who had been assigned to the site-directed care arm to offer Relay services.

All patients (in the study or otherwise) can receive the full range of services offered at the individual study ED per existing protocols at each site.

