7.1 Study Procedures/Evaluations

Study procedures/evaluations in this protocol include: screening, consent, enrollment, randomization, research interviews (self-reported assessments and semi-structured qualitative interviews), overdose prevention education, as well as data extraction from administrative data sets and Relay programmatic data. All participants receive standard medical care in the ED. Those in the Relay intervention arm additionally receive the DOHMH Relay program, and those in the SDC arm additionally receive RA-delivered OD prevention education. There are no laboratory results, biospecimens, or images collected as part of this research protocol.

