Enrollment and informed consent. RAs will enroll and obtain consent from eligible patients for participation in the research activities. The RA will explain the study procedures and incentive schedule, answer any questions, and offer enrollment. Patients will be informed that the decision to participate in the research is voluntary and will not affect the medical care they receive from the ED. If the patient is willing to participate and signs the informed consent form, only then will study staff commence collecting additional information. The informed consent process will be conducted in-person on a study iPad using REDCap (using electronic consent/signature). The participant will be given a paper or e-mailed copy (through REDCap) of the informed consent form and key information sheet. If the patient declines to participate in the study, the RA will call the Relay peer navigator to inform him/her of the patient who has declined to participate in the study but who could potentially receive Relay services (apart from the study, as part of standard DOHMH Relay practice).

Randomization. Patients who meet eligibility criteria and agree to participate in the study will be randomized to the SDC vs. Relay arm. The RA will use an electronic system (REDCap) to create a random assignment to a treatment arm. Randomization uses a 1:1 ratio and is stratified by site; permuted blocks with variable blocks of size 4 and 6 will be used to maintain balance over time and prevent prediction of assignment by the RA. Upon randomization, the RA will immediately inform the participant of the treatment arm assigned. For Relay arm participants, the RA will then inform the Relay peer navigator by phone. If the participant is assigned to the Relay arm, the peer navigator will generally arrive at the ED within 30 minutes.

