
Finally, we will assess the impact of intervention dose, measured using the number, type (phone or in-person conversation, accompaniment to appointments), and duration of contacts; this information is routinely logged by the Relay peer navigator. We will examine the impact of dose using instrumental variables (IV) regression; this approach can substantially increase the strength of causal inference about a variable (such as dose) not fully under experimenter control. IV regression requires a variable related to a dose, but not correlated with any other determinants of dose. Random assignment to study condition meets these requirements; thus, IV regression illuminates the intervention's effectiveness at different dose levels.

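### The instrumental-variable dose paragraph misstates the instrument condition and claims dose-level effects that one binary instrument cannot identify

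*Combined protocol and SAP*

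**What the plan says.** The closing paragraph of Section 10.4.8 (Additional Sub-Group Analyses) will assess intervention dose, "measured using the number, type (phone or in-person conversation, accompaniment to appointments), and duration of contacts". On method it says that "IV regression requires a variable related to a dose, but not correlated with any other determinants of dose", and it concludes: "Random assignment to study condition meets these requirements; thus, IV regression illuminates the intervention's effectiveness at different dose levels". It names no single dose variable, functional form, target parameter or second instrument. It does not mention exclusion.

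Four other places bear on this:

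- Section 7.3.1: "Randomization uses a 1:1 ratio and is stratified by site". There are two arms, so the instrument takes two values.
- Section 7.1: "those in the SDC arm additionally receive RA-delivered OD prevention education". Section 6.1 adds that SDC participants get a printed list of treatment programs and a flyer with a number to call for Relay services.
- Section 6.1, on SDC participants who call that number: "DOHMH and research staff will track any Relay services provided in this patient-initiated manner". Dose in the SDC arm is therefore not zero by design, but it is recorded.
- Section 10.3 makes the primary analysis ITT. Section 10.1 calls the statistical approaches preliminary.

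**The concern.** There are two separate problems.

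The first is the stated condition. What makes an IV estimate causal is the relation of the instrument to the outcome: no shared causes with it, and no path to it except through the exposure. Being uncorrelated with other causes of dose is a different property, and meeting it does not validate the analysis. Because the plan checks assignment only against that property, "Random assignment to study condition meets these requirements" reads as if nothing remained to be assumed. Exclusion does remain to be assumed.

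The second is the conclusion drawn. Effects at several dose levels are several unknowns, and one binary instrument supplies one contrast. The same shortage arises if number, type and duration are treated as three exposures.

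At stake is how the result is read. Section 2.2 says the health department wants evidence on whether to modify, replace or expand Relay. The plan presents this analysis as a way to strengthen causal claims about dose. A single slope could then be taken as evidence on how much peer contact is needed, although the dose shape came from the model and not from the data.

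**Working it through.** The documents give no figure for this analysis, so there is nothing to reproduce. The check is on identification.

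**Inputs.** From Section 10.5: event rates of 2.0 per year in SDC and 1.52 in Relay, a difference of 1.52 - 2.0 = -0.48. This is the power-calculation alternative, used here only for scale. Assumed, because no document gives a contact distribution: one quarter of Relay participants each have 0, 1, 4 or 12 contacts, and SDC participants have none.

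**Step 1: the estimator.** With one binary instrument,

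IV slope = (difference in mean outcome between arms) / (difference in mean dose between arms).

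Mean dose in Relay = (0 + 1 + 4 + 12)/4 = 4.25. Slope = -0.48/4.25 = -0.113 events per contact. The implied effects are -0.11 at 1 contact, -0.45 at 4 and -1.36 at 12.

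**Step 2: three truths with the same slope.** Each is scaled so that the arms differ by -0.48.

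| Truth | Scaling | Effect at 1 | Effect at 4 | Effect at 12 |
|---|---|---|---|---|
| Linear in contacts | -0.48/4.25 = -0.113 per contact | -0.11 | -0.45 | -1.36 |
| All benefit from any contact | -0.48/0.75 | -0.64 | -0.64 | -0.64 |
| Benefit only at 10 or more | -0.48/0.25 | 0 | 0 | -1.92 |

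Numerator and denominator are the same in each row, so the slope is -0.113 every time. It is right at each dose in the first row only.

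**Step 3: a different assumed distribution.** A simulation of 2,000,000 participants used over-dispersed Poisson contacts, 5% SDC crossover and a difference in mean dose of 3.96 contacts. Four shapes gave slopes of -0.1209 to -0.1215, implying about -0.24, -0.61 and -1.21 at 2, 5 and 10 contacts. The true effects at those doses were the same for the linear shape, -0.53 throughout for any contact, and -0.74, -0.74 and 0 for benefit at 1 to 5 contacts only. The fourth shape, a threshold at 8 contacts, needed an effect of -3.94. That exceeds the 2.0 base rate, so it shows only the algebra.

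**Step 4: three dose measures together.** With an intercept, the model has 4 parameters. The constant and assignment supply 2 moment conditions. The cross-product matrix has rank 2, so the parameters are not identified.

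**Step 5: exclusion.** If assignment has a direct effect d on the outcome outside dose, the slope is off by d/(difference in mean dose), which is d/0.48 as a share of the slope. For assumed d of 0.05, 0.10 and 0.20 events, the shares are 0.05/0.48 = 10%, 0.10/0.48 = 21% and 0.20/0.48 = 42%. The documents give no value for d.

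**The case against.** The strongest reply has five parts.

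- **The result need not be wrong.** A reader might infer that the dose conclusion will be false. The documents do not support that. If dose is one scalar, its effect is linear and exclusion holds, the slope is right. The misworded condition does not alter the estimator, and randomization supplies independence from outcome determinants. This stands: the dose-level reading is unsupported, not shown to be false.
- **Exclusion is threatened, not shown to fail.** Section 2.3.2 intends overdose education and naloxone in both arms. Under Section 6.1, Relay peers give overdose education, and a kit if the ED has not, so that content largely balances. This stands in part. Smaller differences remain: the RA-delivered session, the list and the flyer in SDC, and Relay participants who never meet a peer. Separately, if number of contacts is the dose, assignment also shifts type and duration.
- **The plan does not say that the three measures enter one model.** Correct. It leaves the dose variable undefined, and Step 4 applies only to a joint model. The dose-level claim fails under any definition with several levels unless a shape is assumed or instruments are added.
- **The illustration is invented.** The contact distribution is assumed. A quarter of the Relay arm with no contact sits uneasily with delivery in the ED, and zero SDC dose ignores self-referral. The -1.92 effect would remove 96% of a 2.0 rate (1.92/2.0). The numbers show that different truths can share one slope; they do not forecast bias.
- **The analysis is additional and the plan preliminary.** Section 10.1 permits a later correction but makes none, and nothing elsewhere repairs the paragraph. The mediation text in the same section does state its assumptions in terms of the outcome and plans a sensitivity analysis, so the dose paragraph can be held to the same standard.

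**Conclusion.** The paragraph is wrong as written on two counts: the instrument condition, and the claim to show effects at different dose levels. Both follow from the design and do not depend on the assumed contact counts. Assignment identifies one weighted-average effect of one scalar exposure, given relevance, independence, exclusion and monotonicity. Anything about particular dose levels, or about number, type and duration separately, needs an assumed shape or further instruments, and the plan offers neither.

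The size cannot be stated from the documents. Under the assumed 0/1/4/12 distribution, an implied effect of -0.11 at one contact is compatible with a true effect of -0.64 or of 0. The ITT result, which answers whether Relay works, is untouched. The documents tie the health department's decisions to Relay's effectiveness; they do not say that this analysis will set a contact target.

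**What to change.** Rewrite the paragraph as follows.

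1. State four conditions: assignment changes the exposure (relevance); it is independent of other determinants of the outcome; it affects the outcome only through the exposure (exclusion); and it lowers no one's exposure (monotonicity). Say that randomization gives the second and not the third.
2. Pre-specify one scalar exposure, counting Relay services received by SDC participants, and report one average effect. This can be a complier average effect of any peer contact, or an average per-unit effect under a stated linear form. For any contact, the estimate is the ITT difference divided by the difference in the proportion contacted. If that difference were 0.75 to 1.00 (assumed), a difference of -0.48 would become -0.64 to -0.48, so near-universal contact in Relay would add little to ITT. Any contact also treats one self-referred call like 90 days of navigation, which is a further reason for item 4.
3. Delete the claim about different dose levels. Report number, type and duration of contacts within the Relay arm as description, labelled non-causal.
4. Add a sensitivity analysis for a direct effect d of assignment outside the chosen exposure: (ITT difference - d) divided by the difference in mean exposure, over a stated range of d.

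The cost is revised wording and a little more analysis. No new data are needed, since contacts in the Relay arm and self-initiated services in SDC are already tracked. The trial gives up a dose-response claim that its design cannot support.

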10.4.9 Multiple Comparison/Multiplicity

Not applicable.

10.4.10 Tabulation of Individual Response Data

All planned analyses use aggregate data. Individual data will not be published.

CONFIDENTIAL

This material is the property of the NYU School of Medicine and NYU Langone Health. Do not disclose or use except as authorized in writing by the study sponsor
Behavioral Intervention Template Version: 11 January 2019

10.4.11 Exploratory Analyses

Participants will be asked about any services received from an outpatient medical or mental health provider, or from a harm reduction program; for those reporting receipt of any services, we will measure the frequency of contact and the nature of services received. We will additionally assess use of naloxone by participants and naloxone carrying by friends/family. Death from OD, opioid-related OD, and any cause will be tracked using Vital Statistics and/or National Death Index records (accessed by DOHMH) since prior research shows high rates of death, including those unrelated to OD, among patients following ED visits for non-fatal opioid OD.⁴⁸

10.5 Sample Size

The sample size for this study is 350. Our preliminary data indicate the average number of opioid-related adverse events per year in SDC arm will be in the range of 2-3 events/person; this rate is substantiated in the literature.^{19,50,52,58} We wish to be able to detect a decrease in this number of approximately 25% in the Relay arm, a modest effect size judged to be of public health significance. Using a Poisson regression model for the total number of events, 350 participants provide more than 80% power to detect this difference. Specifically, we have 83% power to detect a decrease in the mean event rate from 2.0 per year in SDC to 1.52 in Relay (an incidence rate ratio (IRR) of 1.32 and a 24% reduction). If average opioid-related adverse events in the SDC arm are lower than anticipated, we still have 80% power to detect a decrease in the mean event rate from 1.75 per year in SDC to 1.32 in Relay (IRR = 1.33; a 25% reduction). All calculations assume a two-sided, 0.05-level test, and conservatively include adjustment for possible overdispersion in the primary outcome (overdispersion parameter = 1.6). While formal power and sample size calculations were based on our primary outcome, given that secondary outcomes are generally more common than our primary outcome (e.g., all-cause ED visits) or are time to events expected not to be rare (e.g., time to opioid-involved OD), we expect to have adequate power for secondary outcome analysis as well.

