4.2 Study Endpoints

4.2.1 Primary Study Endpoints

The primary endpoint is the number of opioid-related adverse events in the 12 months following the index ED visit. Opioid-related adverse events include: any opioid-involved OD (fatal or nonfatal) or any other substance use-related ED visit.

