Relay offers motivational counseling as well as sustained peer navigation that provides support and access to services that could help individuals reduce their OD risk behaviors. As such, we expect to detect greater reductions in risk behaviors in the Relay compared to the SDC arm. We will measure OD risk behavior using questionnaires that were developed by a group of OD researchers based on knowledge of OD behavioral risk factors and used in 3 prior studies to capture OD risk behavior.^{49,50,52} These questions measure the frequency, in the past 3 months, at which individuals: 1) used >1 opioid; 2) used benzodiazepines, alcohol, or cocaine/stimulant within 2 hours of an opioid; 3) used alone or behind a locked door; 4) used in a place they had never used before; and 5) used more than usual amount. The total risk score is an aggregation of responses to the individual questions.

Time to next OD is measured using self-report. Frequency of ED visits for any cause (including visits that are not substance use-related) will be measured to assess whether there are differences in overall acute care use representing potentially negative health events. Additionally, we will examine frequency of ED visits for opioid OD and frequency of ED visits for other (non-OD) substance use reasons. These three ED visit secondary endpoints will be count outcomes using administrative data at 12 months and based on documentation of visit diagnosis (including primary and secondary diagnosis ICD codes, text diagnosis, and/or chief complaint). Self-reported opioid-involved OD is based on participant self-report in the 1-, 3- and 6-month follow-up visits and includes nonfatal ODs that did or did not result in an ED visit.

We will also examine multiple potential mediators and moderators of Relay program effectiveness as further described in later sections.

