10.4.2 Analysis of the Primary Efficacy Endpoint(s)

The primary endpoint is the number of opioid-related adverse events in the 12 months following the index ED visit. Opioid-related adverse events include: any opioid-involved OD (fatal or nonfatal) or any other substance use-related ED visit. Overdose deaths are tracked using the DOHMH comprehensive database of NYC overdose deaths. Data on OD resulting in ED visits or other substance use related ED visits will be collected from administrative data at 12 months, as identified from visit chief complaint and/or diagnoses. We will collect additional self-reported data on OD using a questionnaire that has been used in prior studies. This questionnaire will be administered at each study visit. Participants will be asked whether the OD did or did not result in an ED visit. We will use this information to calculate an estimated 12 month opioid-related OD event count.

The primary outcome will be ascertained by administrative data abstraction with adjustment using self-report data as described above. Administrative data extraction will be completed by members of the study team who are blinded to participant arm assignment. Results for the primary outcome will be compared for independent data abstraction completed by two members of the study team; disagreements will be resolved either by consensus or by a study PI.

The primary analysis will use a Poisson generalized linear regression model to evaluate the intervention effect on the total number of opioid-related adverse events. We anticipate the availability of 12 months of follow-up data on all participants but, in the event of death or withdrawal from the study, we will adjust the follow-up time appropriately using an offset term. We will include adjustment for study site, as well as other baseline factors that may be unbalanced across arms. The primary effect measure will be the incidence rate ratio comparing Relay to SDC. Some participants may be routinely high utilizers of the ED, and this may lead to overdispersion of the count outcome; we will therefore use a negative binomial model instead of a Poisson model if warranted.

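### Section 10.5's 83% and 80% power are not reached on its own inputs: about 80% and 77% by the Signorini formula, 76% and 73% by a Wald test

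*Combined protocol and SAP*

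**What the plan says.** Section 10.5 (Sample Size) fixes 350 participants and expects 2 to 3 events per person-year in the SDC arm. It aims to detect a reduction of about 25% with more than 80% power, and gives two specific scenarios:

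- Main: "we have 83% power to detect a decrease in the mean event rate from 2.0 per year in SDC to 1.52 in Relay", described as "an incidence rate ratio (IRR) of 1.32 and a 24% reduction".
- Lower event rate: "we still have 80% power to detect a decrease in the mean event rate from 1.75 per year in SDC to 1.32 in Relay", with a printed IRR of 1.33.

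Both use a two-sided 0.05 test and are said to "conservatively include adjustment for possible overdispersion in the primary outcome (overdispersion parameter = 1.6"). The section names no formula or software and does not define the overdispersion parameter.

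Section 10.6.1 sets 1:1 allocation. Section 10.4.2 expects 12 months of data on everyone and defines the direction of the effect: "The primary effect measure will be the incidence rate ratio comparing Relay to SDC".

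On secondary outcomes, section 10.5 expects adequate power because "secondary outcomes are generally more common than our primary outcome (e.g., all-cause ED visits) or are time to events expected not to be rare".

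**The concern.** Both power figures can be checked from the stated inputs, and standard formulas applied in the planned direction return lower values. The second scenario matters more, because it is the protocol's reassurance that power holds at 80% if events are fewer than expected. If that power is overstated, a null result would be read against a sensitivity the trial did not have.

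Two smaller points sit beside this:

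- The printed IRRs of 1.32 and 1.33 are SDC to Relay, the inverse of the measure fixed in section 10.4.2.
- The rationale that secondary outcomes are generally more common does not fit two of them. Section 4.2.1 defines the primary count: "Opioid-related adverse events include: any opioid-involved OD (fatal or nonfatal) or any other substance use-related ED visit". Section 4.2.2 lists as secondary outcomes: "we will examine frequency of ED visits for opioid OD and frequency of ED visits for other (non-OD) substance use reasons". Both are components of the primary count, so neither can exceed it.

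**Working it through.** **Inputs.** N = 350, two-sided alpha 0.05 (z = 1.96), Poisson regression, overdispersion 1.6 and both pairs of rates come from section 10.5. Allocation 1:1, so 175 per arm, comes from section 10.6.1. One year of follow-up for all comes from section 10.4.2. Assumption: 1.6 multiplies the Poisson variance (variance = 1.6 × mean).

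**Signorini formula** (binary covariate, half in each arm, SDC as base, RR = Relay/SDC):

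power = Φ{ [√(N · rate · (ln RR)² / 1.6) − 1.96·√4] / √(2 + 2/RR) }

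- 2.0 to 1.52: RR = 0.76, ln RR = −0.2744. The square-root term is 5.740 and the denominator √4.632 = 2.152. (5.740 − 3.920)/2.152 = 0.846, so power = **80.1%** (printed 83%).
- 1.75 to 1.32: RR = 0.7543, ln RR = −0.2820. The square-root term is 5.517 and the denominator √4.652 = 2.157. (5.517 − 3.920)/2.157 = 0.741, so power = **77.1%** (printed 80%).

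**Wald test on the log rate ratio**, SE = √[1.6 · (1/(175·r₀) + 1/(175·r₁))]:

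- 2.0 to 1.52: SE = 0.1029; 0.2744/0.1029 − 1.96 = 0.707, so power = **76.0%**.
- 1.75 to 1.32: SE = 0.1102; 0.2820/0.1102 − 1.96 = 0.598, so power = **72.5%**.

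**Simulation.** With 60,000 trials, 175 per arm, variance 1.6 × mean and a quasi-Poisson test, power was 76.1% and 72.5%. A separate run of 40,000 trials gave 76.4% and 73.0%, with a type I error of 5.0%.

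**Other methods in the planned direction** (main / lower-rate scenario): pooled-null log test 76.6% / 73.2%; difference in means 76.3% / 72.8%; square-root transform 76.5% / 73.0%; event-based 76.8% / 73.4%.

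**What would give the printed figures**

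| | 83% at 2.0 to 1.52 | 80% at 1.75 to 1.32 |
|---|---|---|
| Total N, Signorini | 379.0 | 378.2 |
| Total N, Wald | 417.8 | 419.8 |
| Variance multiplier at N = 350, Signorini | 1.48 | 1.48 |
| Variance multiplier at N = 350, Wald | 1.34 | 1.33 |

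The 355 expected enrolments in section 5.6 do not close the gap: Signorini gives 80.6% and 77.6%.

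**Reading 1.6 differently.** As a negative binomial dispersion (variance = μ + 1.6μ²), SE = √[(1/r₀ + 1/r₁ + 2·1.6)/175]. Power is then 41.3% and 41.8%, so the variance-multiplier reading is the favourable one of the two.

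**The broader 25% claim** (exact 25% reduction, N = 350)

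| SDC rate | Signorini | Wald |
|---|---|---|
| 1.75 | 78.6% | 74.1% |
| 2.0 | 83.4% | 79.5% |
| 2.5 | 90.3% | 87.6% |
| 3.0 | 94.5% | 92.7% |

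The reduction detectable with 80% power is 24.0% (Signorini) or 25.1% (Wald) at an SDC rate of 2.0, and 25.4% or 26.8% at 1.75. For 80% power at a 25% reduction the SDC rate must be 1.82 (Signorini) or 2.02 (Wald), both above 1.75.

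**The case against.** The strongest reply is that the printed figures can be matched. Keep the SDC rate as base in the Signorini formula but enter the ratio upside down, as the IRRs are printed. With 2.0/1.52 and 1.75/1.32 it returns 83.4% and 80.3%, which round to 83% and 80%. This is a plausible source of the figures and points to Signorini as the formula used, so the smaller shortfall of about 3 points may be the fairer measure. But that calculation describes an increase from 2.0 to 2.63 (or 1.75 to 2.32), not the stated decrease. It also needs unrounded ratios, since the printed 1.32 and 1.33 give 84.3% and 81.2%. With no software named, it remains an inference about the cause and does not rescue the figures. Two other near-matches also fail: a one-sided Wald test (84.7% and 81.9%) contradicts the stated two-sided test, and using the SDC variance in both arms (81.9% and 78.8%) ignores the lower Relay rate.

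The reply is right on several other points:

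- The two formulas differ by about 4 points, more than the whole Signorini shortfall, and the plan does not say which applies.
- More than 80% power for 2.0 to 1.52 just survives by Signorini.
- A 25% reduction is well powered at 2.5 to 3 events per person.
- The 1.75 scenario lies below the expected range.
- The stated rates and percentage reductions keep the direction clear, so the inverted IRR is a labelling fault.
- The remark on secondary outcomes is a hedged expectation, and the point about it is minor.

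Section 10.1 leaves the detailed analysis plan to be finalized, which makes correction easy but does not itself correct the figures.

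**Conclusion.** The concern holds. In the planned direction, with 1.6 as a variance multiplier and complete 12-month follow-up, the design gives 80.1% (Signorini) or 76.0% (Wald) against the printed 83%, and 77.1% or 72.5% against the printed 80%. The chance of missing the stated effect is about 20% to 24% rather than 17% in the main scenario, and about 23% to 27% rather than 20% in the lower-rate scenario. The 80% claim at 1.75 fails under both formulas.

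The size of the shortfall depends on the formula, and the variance-multiplier reading is an assumption; the negative binomial reading is far less favourable. The cause cannot be established from the documents. The primary test, its significance level and the planned model are unaffected. This should be fixed, but it does not undermine the trial's main design claim.

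**What to change.** Revise the wording of section 10.5:

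1. Name the power formula and state that 1.6 multiplies the Poisson variance.
2. Give the rate ratios as Relay to SDC, 0.76 and 0.754.
3. Replace 83% and 80% with the power under the named formula: 80% and 77% (Signorini) or 76% and 73% (Wald). Alternatively, give the detectable reductions at 80% power for SDC rates of 2.0 and 1.75: about 24% and 25% (Signorini) or 25% and 27% (Wald).
4. Withdraw the statement that 80% power is kept at 1.75 to 1.32.
5. As a minor edit, limit the more-common rationale to outcomes such as all-cause ED visits, and do not extend it to the two component ED counts.

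No extra participants are needed; the cost is a less favourable stated power. Keeping the printed figures instead would need about 380 participants by Signorini (30 more) or 418 to 420 by Wald (about 70 more).
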